8.4 Analysis Sets

Intention-to-Treat Analysis Set (Full Analysis Set)

The Intention-to-Treat (ITT) Analysis Set will include all subjects randomly allocated to a treatment, based on the intention to treat “as randomized” principle (i.e., the planned treatment regimen rather than the actual treatment given in case of any difference).

Modified Intention-to-Treat Analysis Set

The Modified ITT (mITT) Analysis Set will include all subjects from the ITT Analysis Set who have a baseline and at least one post-treatment MRI assessment available.

Per-Protocol Analysis Set

The Per-Protocol (PP) Analysis Set will include all subjects from the mITT Analysis Set who have been treated according to the clinical trial protocol and fulfill the following criteria:

- Compliance with all entry criteria
- Absence of major clinical trial protocol violations with respect to factors likely to affect the efficacy of treatment, where the nature of such clinical trial protocol violations will be defined before breaking the blind
- Adequate compliance with trial medication (this will be defined in the SAP)

Safety Analysis Set

The Safety Analysis Set will include all subjects who receive at least one dose of trial treatment. Subjects will be analyzed according to the actual treatment they receive.

Pharmacokinetic Analysis Set

The PK Analysis Set will include all subjects from the Safety Analysis Set with at least one available serum or synovial fluid measurement.

Subgroup Analyses

Subgroup analyses (especially for the analysis of the primary endpoint) will be considered for categories including Kellgren-Lawrence grade (Grade 2, Grade 3), sex (Male, Female), age (< 65 years old, \geq 65 years old), body mass index (BMI; < 30 kg/m², \geq 30 kg/m²), and country.

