8.5.5 Analysis of Further Endpoints

The following domains will be described overall and by treatment group using summary statistics:

- Disposition of subjects and discontinuations
- Protocol deviations
- Demographics, medical history, and other baseline characteristics
- Past and concomitant medications and procedures, with particular attention to pain medications
- Treatment compliance and exposure, as assessed by the number of injections received

PK sample bioanalysis will be performed by Merck Serono NCD-DMPK; and PK data analyses, as well as investigation of the relationship between dosing (dose and regimen), cartilage structure, and clinical scores as a function of time will be performed by Merck Serono Exploratory Medicine.

Exploratory biomarker sample and data analyses will be performed under the responsibility of Merck Serono NCD – Biomarker Technologies. The sample analytes will be further specified in the Manual of Procedures (MOP), and data analysis will be described in an Exploratory Biomarkers Statistical Analysis Plan (SAP). Results will be reported separately in an Exploratory Biomarkers Report.

Analysis of Data from the Extended Follow-up Phase

Data reported during the extended follow-up phase will be presented mainly using descriptive statistics.

Exploratory Pharmacometric Modeling

A modeling analysis will be performed in order to evaluate the disease-modifying effect of sprifermin, i.e., improvement of cartilage structure and clinical symptoms (WOMAC).

In particular, the relationship between cartilage structure changes and improvement of clinical symptoms will be investigated, in order to support the selection of the optimal dose/dosing regimen for future trials.

In order to derive a better understanding of sprifermin effects, other potential influencing/confounding factors such as the placebo effect will be included in the model.

The development of the models implies a covariate analysis to explore the influence of various potential predictors of variability, e.g., demographics/anthropometrics, biomarkers (including PGt markers), and concomitant medications.

Finally, simulations will be performed to address various scenarios, to support decision making and planning of future studies.

Additional models focusing on other secondary/exploratory endpoints could be developed if deemed appropriate.

The details of modeling and simulation analyses will be described in a Modeling and Simulation Data Analysis Plan.

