- Change from baseline in serum, urine, and synovial markers associated with administration of the compound
- Baseline biochemical biomarkers and/or genetic markers associated with response to treatment or disease progression (response assessed by MRI, X-ray and/or questionnaire)
- Changes in MRI outcomes, WOMAC scores, 20-meter walk test, PGA, PGIC, JSW, OMERACT-OARSI responder rate, KOOS QOL, KOOS Symptom Index, MOS SF-36, NRS pain score in the target and contralateral knee, presence of pain in other joints, ICOAP, safety laboratory values, and vital signs over the extended follow-up period and nature, incidence and severity of local and systemic AEs during the extended follow-up period (to be summarized descriptively)
- Relationship between dosing (dose and regimen), cartilage structures, and clinical scores as a function of time

Trial Design	This is a multicenter, randomized, double-blind, placebo-controlled, parallel-group Phase II trial of sprifermin administered i.a. in subjects with primary OA of the knee and Kellgren-Lawrence (KL) grade 2 or 3.
	The trial consists of a screening period lasting up to 42 days, a 2-year (104-week) double-blind placebo-controlled (DBPC) treatment phase, which will start at randomization (Week 0/Visit 2) and a 3-year extended follow-up phase. Please see table 5 and 6 (Appendix E) in the clinical trial protocol. Please see below for specification of dose groups (Trial Product).
Number of Subjects	The trial will randomize approximately 545 subjects (109 per treatment group).
Trial Product	Sprifermin (also known as: recombinant human fibroblast growth factor 18 [rhFGF-18]; AS902330) 30 mcg or 100 mcg, administered intra-articularly (i.a.).
	Subjects will receive 4 cycles of treatment (each consisting of 3 once-weekly i.a. injections over 3 consecutive weeks) at intervals of 6 months.
	Subjects will be randomized in equal allocation to one of 5 treatment groups:
	• 4 cycles of sprifermin (100 mcg per injection, total dose 1200 mcg)
	• 2 cycles of sprifermin (100 mcg per injection) alternating with 2 cycles of placebo (total dose 600 mcg)
	• 4 cycles of sprifermin (30 mcg per injection, total dose 360 mcg)
	• 2 cycles of sprifermin (30 mcg per injection) alternating with 2 cycles of placebo (total dose 180 mcg)
	• 4 cycles of placebo (total dose 0 mcg)
Treatment and Trial Duration	Planned treatment duration is 2 years.
	Follow-up duration is 3 years.

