The Intention-to-Treat (ITT) Analysis Set will include all randomized subjects and will be reported in any analysis "as randomized" i.e. only the planned treatment regimen is used. (i.e., the planned treatment regimen rather than the actual treatment given in case of any difference). This analysis set will be used for all non-MRI efficacy evaluations (symptoms and X-ray based endpoints).

Modified Intention-to-Treat Analysis Set

The Modified ITT (mITT) Analysis Set will include all subjects from the ITT Analysis Set who have a baseline (prior to first injection) and at least one post-treatment quantitative MRI assessment available in the DBPC part (up to and including day 819). This analysis set will be used for all MRI efficacy evaluations.

Per Protocol Analysis Set

The Per-Protocol (PP) Analysis Set will include all subjects from the mITT Analysis Set who have been treated according to the clinical trial protocol and fulfill the following criteria:

- Compliance with all entry criteria (fulfilling all inclusion criteria and no exclusion criteria)
- Absence of major clinical trial protocol deviations with respect to factors likely to affect the efficacy of treatment, such as non-missing and valid baseline and post-baseline measurement of the primary efficacy endpoint (quantitative MRI), where the nature of such deviations will be defined before or at the Blind Data Review Meeting (before breaking the blind) for the reporting of the treatment phase, in collaboration between the medical, clinical and statistical responsible person (see also Section 8).

Major protocol deviations affecting efficacy include: Prohibited medication/procedures during the treatment period and inadequate treatment compliance i.e. deviations from the planned amount of active dose and schedule of treatment (out of allowed window as specified in the "Analysis Sets" document). In order to be compliant the inter-cycle window should be within 140 to 196 days, and the intra-cycle window should be 5 days or above. Subjects who have (actual total dose)/(planned total dose)*100 within 75-100 % will be considered treatment compliant. If subject was randomized to placebo group but instead received at least one dose of sprifermin, then this subject will be classified as having major protocol deviation. A comprehensive list of all deviations and the process to identify each type of deviation are provided in the "Analysis Sets" document that will be finalized prior to Year-2 database lock.

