12.1 Protocol Deviations

A table will be produced summarizing, by treatment group, the number and percentage of subjects with a major protocol deviation, overall and by type of deviation (ITT and mITT Analysis Sets).

All protocol deviations will be listed and each will be marked whether it is major or minor. Major clinical deviations who affect efficacy will result in exclusion from the PP Analysis Set.

Major protocol deviations affecting efficacy include: Prohibited medication/procedures during the treatment period and inadequate treatment compliance i.e. deviations from the planned amount of active dose and schedule of treatment (out of allowed window as specified in the "Analysis Sets" document). Subjects who have (actual total dose)/(planned total dose)*100 within 75-100 % will be considered treatment compliant. If subject was randomized to placebo group but instead received at least one dose of sprifermin, then this subject will be classified as having major protocol deviation. Additionally subjects identified in the Note To File: "NTF_QC of primary endpoint MRI FORWARD 17MAY2016", will be excluded from the PP.

13 Demographics and Other Baseline Characteristics

Demographics and other baseline characteristics will be presented descriptively for the analysis sets described in table 2 (Section 10). Moreover, demographics will be presented by country.

By-subject listings accompanying each demographic and baseline characteristics table will be produced.

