15 Treatment Compliance and Exposure

Exposure to sprifermin will be summarized descriptively in terms of:

- Duration of exposure = date of last injection date of first injection +1
- Total dose (μg)= sum of (number of X μg dose injections * X μg)
- Listing of treatment exposure including time between injections within a cycle and time between last injection of previous cycle and first injection of next cycle will be provided.

Treatment compliance will be summarized descriptively in terms of:

• Mean number of injections by cycle and overall;

- Number of subjects (and percentage) receiving 1,2,3....12 injections; and
- Number of subjects (and percentage) with 75-100 % treatment compliance. Subjects who have (actual total dose)/(planned total dose)*100 within 75-100 % will be considered treatment compliant. Treatment compliance will not be summarized for the placebo group.
- Listing of subjects receiving wrong medication will be provided.

16 Endpoint Evaluation

This section presents specifications for analyzing the trial endpoints specified in the Clinical Trial Protocol to meet the trial objective. Endpoints not identified in the Clinical Trial Protocol are also presented here.

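### The Per-Protocol dose-compliance ratio is 0/0 on placebo and needs treatment codes, and the SAP states no dose criterion that placebo subjects can meet or fail by missing injections

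*SAP*

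**What the plan says.** Protocol 8.4 makes medication compliance a condition of the PP set and leaves the definition open: "Adequate compliance with trial medication (this will be defined in the SAP"). Protocol 8.5.5, listing what will be described, names the measure: "Treatment compliance and exposure, as assessed by the number of injections received".

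SAP Section 10 supplies the definition: "Subjects who have (actual total dose)/(planned total dose)*100 within 75-100 % will be considered treatment compliant". Sections 12.1 and 15 repeat it. Sections 10 and 12.1 make clear that the dose is sprifermin, because inadequate compliance means "deviations from the planned amount of active dose and schedule of treatment". SAP Section 6 gives the planned placebo exposure: "4 cycles of placebo (total dose 0 mcg").

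The only dose rule in Section 10 written for placebo concerns wrong treatment ("If subject was randomized to placebo group but instead received at least one dose of sprifermin"), which is a major deviation. Missed placebo injections are not mentioned. Section 15 adds: "Treatment compliance will not be summarized for the placebo group". That settles a table, not PP membership.

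On timing, SAP 8.1 has exclusions decided while the data are still blinded, and Section 10 has deviations finalised before unblinding. SAP 16.1 then repeats both primary tests (linear trend and overall effect) on the PP set. Appendix 19.5.2 also lists PP versions of the compartment thickness, joint space width and WOMAC tables.

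**The concern.** There are two problems.

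First, the stated threshold cannot be evaluated in the control arm. If the text is followed literally, sprifermin subjects are selected on the share of active drug received and placebo subjects are not selected on any dose measure. A robustness check is then run on groups chosen by different rules. If the gap is instead closed case by case at the data review meeting, the control arm of PP rests on an unwritten rule.

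Second, both parts of the ratio depend on the arm and on which cycles were active. Blinded injection records do not determine it. For the Safety set the SAP explicitly describes a step taken after unblinding. For PP it describes neither such a step nor a separate unblinded party.

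Early placebo stoppers can reach the PP set. Protocol 7.1.5 gives subjects who stop treatment the Week 104 assessments, MRI included, at the time they stop. SAP Table 3 assigns any MRI on days 2-224 to Week 26. One such scan plus a baseline scan is enough for mITT, from which PP is drawn.

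**Working it through.** **1. Planned doses reproduce.** From Protocol Table 1, dose = 3 injections x active cycles x mcg per injection:
- 3 x 4 x 100 = 1200
- 3 x 2 x 100 = 600
- 3 x 4 x 30 = 360
- 3 x 2 x 30 = 180
- placebo 0

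All match the plan. Every arm has 12 injections. The alternating arms are active in Cycles 1 and 3.

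**2. The ratio for a subject who stops after k injections (correct kits).**

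| k | 4-cycle arms (k/12) | alternating arms (active/6) | placebo |
|---|---|---|---|
| 6 | 50.0% out | 3/6 = 50.0% out | 0/0 |
| 7 | 58.3% out | 4/6 = 66.7% out | 0/0 |
| 8 | 66.7% out | 5/6 = 83.3% in | 0/0 |
| 9 | 75.0% in | 6/6 = 100% in | 0/0 |
| 12 | 100% in | 100% in | 0/0 |

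Anyone who completes Cycle 3 stays in PP in every sprifermin arm. The question therefore concerns earlier stoppers and subjects with several missed injections.

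**3. How many subjects the ratio removes per sprifermin arm.** Inputs: 109 per arm and 30% dropout (Protocol 8.1). Assumption: stopping is spread evenly over 104 weeks. The ninth injection falls at Week 54 and the eighth at Week 53.
- 4-cycle: 0.30 x 54/104 x 109 = 17.0
- alternating: 0.30 x 53/104 x 109 = 16.7
- stoppers before Week 26: 0.30 x 26/104 x 109 = 8.2. If they have no post-treatment MRI they are outside mITT already, leaving 8.8 and 8.5.

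The range is about 9-17 of 109.

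**4. Effect on the placebo mean if the matching placebo subjects stay.** These subjects contribute early MRI visits only. In the repeated-measures model an early difference d carries to Week 104 roughly in proportion to the correlation rho, so shift = f x rho x d.
- f (their share of the placebo arm): 8.8/100.8 = 0.087 to 17.0/109 = 0.156
- rho: 0.5-0.8 (assumption)
- d: 0.01-0.03 mm (assumption; 0.03 mm is the whole placebo change assumed in Protocol 8.1)
- low: 0.087 x 0.5 x 0.01 = 0.0004 mm
- high: 0.156 x 0.8 x 0.03 = 0.0037 mm

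Generalised least squares on the four MRI visits with monotone dropout (compound symmetry 0.5 and 0.8, AR(1) 0.8) gives 0.0004-0.0040 mm.

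**5. Against the planned trend contrast.** With the assumed means, -2(-0.03) - 1(-0.01) + 0(0.01) + 1(0.01) + 2(0.03) = 0.14. Placebo has coefficient -2, so the relative effect is 2 x 0.00044/0.14 = 0.6% to 2 x 0.00397/0.14 = 5.7%.

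**6. What a count of 9 of 12 does.** It is defined in all five arms and needs no codes. In the 4-cycle arms with correct kits it equals the present rule (9/12 = 75%). Alone it is not enough in the alternating arms. A subject who misses the last two injections of Cycle 1 and the last of Cycle 3 has 9 of 12 injections but 3/6 = 50% of active dose. Nor does a count see wrong kits: twelve 30 mcg kits in the 1200 mcg arm give 360/1200 = 30%.

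**The case against.** **Another rule may cover placebo.** SAP Section 10 refers the full list of deviations, and how each is identified, to the Analysis Sets document, which may hold a placebo criterion or a firewalled derivation. The opening PP condition ("who have been treated according to the clinical trial protocol and fulfill the following criteria") and the schedule windows apply to every arm, so placebo is not free of all compliance checks. Section 10 also gives a valid post-baseline MRI as a PP factor. If that means a 2-year scan, a placebo subject who stopped before Week 54 would leave anyway, because the discontinuation scan falls outside days 589-819. Each is possible, and any of them would take the bias to near zero. None is stated as the placebo counterpart of a numerical threshold that the SAP gives three times. The window rule is also unclear for someone who stops for good, and it sets no upper limit within a cycle.

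**Different verdicts for the same injection record.** A reader might infer that the ratio is wrong because 8 injections fail in a 4-cycle arm and pass in an alternating arm. Over all 4096 received/missed patterns, 573 pass in at least one sprifermin regimen and 399 of those fail in the other. The documents do not support calling this an error. The primary hypothesis is ordered by total sprifermin dose, and a missed placebo injection does not change that dose. The count also weights every pattern equally. At an assumed independent miss rate of 5% or 10% per injection, only about 3% or 10% of subjects have a discordant record.

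**Conflict with the protocol.** A reader might also infer that the SAP contradicts Protocol 8.5.5. It does not: Protocol 8.4 delegates the PP definition, and 8.5.5 concerns descriptive summaries. It shows only that an injection count is a measure the plan already recognises.

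**Blinding.** A pre-specified algorithm would make the ratio workable without replacing it. That is right, and the fix uses it.

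**Conclusion.** The point holds. On the SAP text, PP dose compliance has no value in one of five arms, and the criterion needs information that those deciding exclusions are not meant to have. Following the text selects sprifermin subjects on dose and leaves placebo subjects unselected on dose.

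The consequence is limited to the PP sensitivity analyses. The documents give no ground for inferring that the mITT primary result is affected. The size is probably small: 0.6-5.7% of the planned contrast of 0.14, resting on evenly spread dropout, an assumed difference of 0.01-0.03 mm and an assumed correlation of 0.5-0.8. The direction is not known, because nothing in the documents says whether placebo stoppers lose more or less cartilage than those who continue. The text should be corrected before database lock, mainly because an inclusion rule that cannot be evaluated for the control arm leaves PP membership to judgement. Confidence is medium, given that the Analysis Sets document was not available.

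**What to change.** In SAP 10, 12.1 and 15, matched in the Analysis Sets document:

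- Add an injection-count criterion, applied identically and blind in all five arms: at least 75% of the 12 planned injections, that is at least 9 of 12, active or placebo.
- State that a permanent stopper below this count is non-compliant in every arm, placebo included.
- Keep the schedule windows.
- Keep the 75-100% active-dose ratio for the sprifermin arms only, as a dose check run by a pre-specified algorithm or an unblinded party. Step 6 of the working shows why the count cannot replace it.
- Report injection compliance for placebo too.

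The cost is a few sentences. No new data are needed: SAP 15 already plans counts of subjects by number of injections and a listing of wrong medication. The downside is that a few alternating-arm subjects with adequate active dose but fewer than 9 injections leave PP, for example one who stops after the eighth (5/6 = 83.3% of active dose). At an assumed 10% independent miss rate, 88.57% of alternating-arm subjects pass the ratio and 87.94% pass both criteria, a loss of about 0.6 percentage points. The alternating arms also remain selected on active dose in a way placebo cannot be; that residual difference follows from a defensible choice. This changes an analysis definition only, not dosing.
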